5.1.2. Data Handling Rules

This study will obtain mainly 3 types of data for statistical analysis: the smartphone/app-based PRO data, the activity data collected from the Fitbit device and the claims data on adverse events (including clinical outcomes, prescription fills, and related HRU). In addition, participant's self-reported AE data collected via a Call Center will be directly sent over to Janssen Safety separately and is described below as well. All data will be received and processed by PRA (3rd party vendor, see [Appendix 5: CHIEF-HF Study Data Flow Diagram](#)) into analysis files based on specifications provided by the sponsor/study SAP unless specified otherwise.

Smartphone Data - PRO Measures

PRO data (ie, KCCQ, PGIC and PGI-S, participant satisfaction survey) will be collected via the smartphone apps available with participants. Based on the administration of the KCCQ at screening/baseline through an app, an overall summary score will be produced to decide eligibility of individual participant into the study. The individual domains and summary scores of KCCQ will be calculated using the scoring algorithm provided in the KCCQ manual at specified time points during the study. Missingness in these PRO measures may result from participants not completing the questionnaires on the smartphone app at the scheduled times during the study period for various reasons including non-compliance with the protocol, discontinuation due to AE, loss to follow up, etc.

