Missing and incomplete data in KCCQ PRO measure may be of 2 types: missing at the form-level and at the item-level. Form-level missing data refers to a participant missing an entire PRO assessment for a scheduled time point. If not otherwise specified, analyses will be conducted on all available data and form-level missing data will not be imputed. For the KCCQ, derivation of individual domain scores in the presence of missing item-level responses will follow algorithms specified in the KCCQ manual. PRA will calculate baseline KCCQ overall summary score based on the KCCQ app and include in the analysis database. For calculation of all other KCCQ domain scores (including the KCCQ-TSS) at baseline and at all post-randomization time points, scoring instructions available per the KCCQ manual with Janssen will be followed (see Appendix 8). For the PGIC and PGI-S measures, a single imputation (ie, last observed scores carried forward) for missing post-baseline scores will be used as a conservative rule. Vertical file formats will be prepared for all PRO data, reading one record per patient for each measurement time (ie, baseline, Weeks 2, 4, 6, and 12, and Months 6 and 9, respectively).

Fitbit Data - Clinical (Activity) Measures

Data from the Fitbit device pertaining to the daily total step counts and daily total floors climbed will be aggregated over 2-week intervals for the entire study duration (see [Table 1](#)). Due to the general sedentary nature of HF patients, Fitbit recorded <100 steps taken in a day will not be

considered in the calculation of averages for daily step counts . If missing >7 days (50%) in a 2-week interval, the corresponding 2-week interval average will be set to missing.

In case of premature discontinuation of the study intervention, the average of the last non-missing 14-day window prior to the last dose of study intervention will always be used as an EOT value. If the EOT value corresponding to the period (EOT-14, EOT-1) is missing (not valid), the EOT period will be rolled back by one day, ie, (EOT-15, EOT-2), (EOT-16, EOT-3), until a non-missing (valid) value is available. This corresponds to a last observation carried forward (LOCF) up to Week 12/EOT approach. If no post-baseline daily activity data have been collected for at least 7 days over a 14-day time window, no EOT value will be computed, and the post-baseline value will be set to missing.

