For the anchor-based analysis of the KCCQ-TSS endpoint, participants will be characterized based on the PGIC scores at Week 12. The mean change in KCCQ-TSS endpoint observed in the smallest improvement category of the PGIC will be examined as a key anchor-based indicator of a responder. The definition for a small improvement in PGIC is given as those who improve by one category (i.e., from “a little improved” to “somewhat improved”). Specifically, the retrospective PGIC responses of “3=a little improved” will be selected to represent time points where participants register meaningful changes in their HF symptoms. Each time a participant responds with a PGIC score of “3=a little improved”, a KCCQ-TSS change score from the preceding visit is computed. For the double-blind treatment period, the PGIC will be collected at 4 time points (i.e., Weeks 2, 4, 6, and 12 respectively) which can yield between zero and 4 KCCQ-TSS change scores by each participant. For each participant with at least one PGIC response of “3=a little improved”, a mean of the individual participant’s KCCQ-TSS change scores is computed. A summary of KCCQ-TSS change scores across PGIC categories¹⁶ will then be presented.

The KCCQ-TSS change scores may also be standardized into effect size (ES) statistics by dividing them by their SD at baseline. The following cutoff values will be used to interpret effect size: small ES = 0.2, moderate ES = 0.5, and large ES = 0.8. Together with the CDF, results from the anchor-based methods will be examined and a single responder definition threshold will be determined, if the results from the anchor-based assessments in this study differ substantially from prior studies examining the clinical meaningfulness of changes in the KCCQ.

In addition, a distribution-based change (i.e., minimum detectable [MID] change) may be explored for which the KCCQ-TSS can be derived using the baseline SD. Generally, a value of half the baseline SD has been frequently found to correspond to the MID obtained via the anchor-based method. A value of $0.2 \times \text{SD}$ may also be examined.

Subgroup analyses for the change from baseline to Week 12 for the primary effectiveness endpoint will be conducted for subgroups (listed in Section 2.4) based on all randomized analysis set. These analyses will assess consistency of the overall treatment effect across subgroup variables.

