5.4.2. Analysis Methods

The exploratory endpoints listed below will be presented using descriptive statistics at each time point measurements are taken. Where specified, 95% confidence intervals (CIs) and p-values will be presented but no multiplicity adjustment will be made. Analyses of mean changes from baseline to Week 12 and month 9 (Day 252) respectively will be conducted, as described below.

- Appendix 6: Patient Global Impression of Change (PGIC) is a validated generic tool for assessment of overall change in the severity of illness following treatment. Participants rate how they feel now compared with how they felt before receiving study intervention on a 7-point scale where 1 is “Very much improved” and 7 is “Very much worse”. A mean \pm SD PGIC score for each time point will be calculated by randomized intervention group. Distribution of PGIC score at Week 12 will also be presented. Based on the PGIC symmetric scale, a dichotomous scale of “Yes” or “No” will be derived. A favorable change is score of 1-3 = ‘Yes’, which means there is significant improvement with the study intervention. If the response is 4-7 = ‘No’, it is considered no significant change. Change in the KCCQ-TSS from baseline to Week 12 by PGIC response at Week 12 will be summarized by treatment group, and, also graphically displayed (i.e., x-axis will display categories of PGIC response at Week 12 and y-axis will display mean change scores from baseline to Week 12 in KCCQ-TSS by treatment group).
- Distribution of participants in PGI-S (see [Appendix 7: Patient Global Impression of Severity \(PGI-S\)](#)) response categories will be summarized by randomized intervention group at baseline and by Week 12. Mean change in PGI-S score between baseline and Week 12 will be summarized by randomized group. Change in the KCCQ-TSS from baseline to Week 12 by PGI-S response at Week 12 will be summarized.

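### Carrying forward missing PGIC and PGI-S scores is not guaranteed to be conservative, and with no stop at end of treatment it can put on-treatment scores into the Month 6 and Month 9 PGIC means

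*SAP*

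**What the plan says.** SAP 5.1.2 (Data Handling Rules) sets a default for patient-reported outcomes: unless otherwise specified, "form-level missing data will not be imputed". It then makes PGIC and PGI-S the exception: "a single imputation (ie, last observed scores carried forward) for missing post-baseline scores will be used as a conservative rule". It gives no reason for the label, no limit on how long a score may be carried and no sensitivity analysis for these measures. The analysis file holds records at "baseline, Weeks 2, 4, 6, and 12, and Months 6 and 9, respectively".

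The same section expects questionnaires to be missed for "various reasons including non-compliance with the protocol, discontinuation due to AE, loss to follow up, etc". Its step-count rule is also a form of LOCF, but is described as running only up to Week 12 or end of treatment.

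Drug stops after Week 12 (SAP 2.1), and participants are told their allocation at that point (SAP 1.2). SAP 2 analyses exploratory endpoints over both the 12-week period and the full 9 months. SAP 5.4.1 lists mean PGIC over time and PGI-S change to Week 12. The lead-in to SAP 5.4.2 says "Analyses of mean changes from baseline to Week 12 and month 9 (Day 252) respectively will be conducted", and its PGIC item says that a mean and SD "PGIC score for each time point will be calculated by randomized intervention group". SAP 5.4.2 also plans summaries of KCCQ-TSS change by PGIC and by PGI-S response at Week 12.

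**The concern.** An imputation rule is conservative only if it pulls the estimated difference towards no effect. LOCF does not do that in general. It freezes a participant at the last response. Someone who rated themselves a little improved at Week 2 and then left because of an adverse event stays a little improved at Week 12. Under the PGIC dichotomy in SAP 5.4.2, that person also stays in the favourable category. Because the SAP itself expects missing forms from adverse-event discontinuation and loss to follow-up, missingness may depend on both outcome and arm.

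The second problem is the missing stop. Month 6 and Month 9 describe participants off drug and aware of their allocation. A participant with no score after Week 12 contributes a score given on treatment and under blinding. Part of any Week 12 difference is then copied into the follow-up means, where it can look like a persisting effect.

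The third is narrower. In the Week 12 displays of KCCQ-TSS change by global rating, a participant who completed the KCCQ but not the rating would be placed in a category by a score from another visit.

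At stake is the reading of exploratory results, under a label that invites more trust than the rule earns.

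**Working it through.** The SAP gives no figure to reproduce here: no missing-data rate, SD or expected effect is stated for PGIC or PGI-S. The only dropout figure is 5% to 10% in SAP 1.4, given for the KCCQ sample size. All means and missing shares below are assumptions.

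**Direction of the bias at Week 12.** Take PGI-S change, canagliflozin minus placebo, with negative values favouring canagliflozin. Let m be the share missing in an arm, L the mean carried score and T the true final mean, taken as the same for those with and without data. Then

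bias = m_cana × (L_cana − T_cana) − m_plac × (L_plac − T_plac).

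- Effect still growing, 10% missing per arm, L = −0.15 and −0.05, T = −0.30 and −0.10: bias = 0.10 × 0.15 − 0.10 × 0.05 = +0.01. True −0.20, LOCF −0.19. Slightly conservative.
- No true effect, both arms worsen by 0.4 after the last score, missing 15% canagliflozin and 5% placebo: bias = 0.15 × (−0.4) − 0.05 × (−0.4) = −0.04. A spurious benefit.
- No true effect, both arms improve by 0.3, missing 5% canagliflozin and 15% placebo: bias = 0.05 × 0.3 − 0.15 × 0.3 = −0.03. With the missing shares swapped it is +0.03.
- 10% stop drug and lose a −0.30 effect, but their on-treatment score is carried: true = 0.90 × (−0.30) = −0.27, LOCF −0.30. Overstated. (Here those with missing scores differ from the rest, so the difference is computed directly.)

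The sign changes with the trajectories and with which arm has more missing data.

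**Carry-over past end of treatment.** Let the Week 12 difference be D, the true off-drug difference 0, and m the share in each arm whose last score dates from the treatment period. Then

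LOCF difference = (1 − m) × 0 + m × D = m × D.

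| D (assumed) | m = 5% | 10% | 20% | 40% |
|---|---|---|---|---|
| 0.2 | 0.010 | 0.020 | 0.040 | 0.080 |
| 0.3 | 0.015 | 0.030 | 0.060 | 0.120 |

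At Month 9, m covers only participants missing both Month 6 and Month 9; someone with a Month 6 score carries that off-treatment value instead.

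**The two LOCF rules in SAP 5.1.2.** For step count, the carried value is the last valid 14-day window before the last dose, and the approach is bounded at Week 12 or end of treatment. For PGIC and PGI-S no bound is written, and the records run to Month 9. Followed as written, the rule crosses the end of treatment.

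**The case against.** The strongest reply is that little hangs on this. Both measures are exploratory, and SAP 5.4.2 plans means, SDs and distributions for them. The PGI-S endpoint is defined only to Week 12, so the Month 9 problem rests on mean PGIC over time and on the general wording of SAP 2 and 5.4.2. Week 12 is itself the end of treatment, so an on-treatment score carried there misleads mainly for those who stopped drug or left early. At the only dropout rates in the SAP, 5% to 10%, the carry-over is 0.01 to 0.03 category. Handling KCCQ differently is a pre-specified exception, not an error. All of that stands and limits the size of the point. It does not justify the label or the missing stop.

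A reader might infer four stronger things that the documents do not support:

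- *That LOCF is anti-conservative here.* The first scenario above is conservative. The direction is unknown.
- *That standard errors are too small, by a factor of √0.8 = 0.89 with 20% missing.* That ratio only compares the full sample with the complete cases. Under LOCF each participant still contributes one independent value, so the ordinary standard error is right for the LOCF mean. A simulation with 220 per arm, 20% missing at random, SD 0.8, visit correlation 0.5 and no effect (all assumed except the sample size, the middle of the 400 to 480 total in SAP 1.4) gave an estimated-to-true standard error ratio of about 1.00 and a 5% rejection rate. The risk is bias.
- *That type I error is inflated by a stated amount.* SAP 1.3 mentions nominal 5% testing of exploratory endpoints, but SAP 5.4.2 defines no test for these two.
- *That the KCCQ-TSS responder anchor is corrupted.* SAP 5.2.3 says "participants will be characterized based on the PGIC scores at Week 12", but its repeated-response step computes a KCCQ change each time a participant actually gives the a-little-improved answer, and a carried score is not a response. What remains is the Week 12 displays in SAP 5.4.2, and there only when the KCCQ was completed and the global rating was not. The documents give no rate for that.

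**Conclusion.** The point holds as a small, cheap correction. SAP 5.1.2 calls LOCF conservative without support, and its bias can go either way. Because the rule does not stop at end of treatment, Month 6 and Month 9 PGIC means by arm can mix off-treatment scores with earlier on-treatment, blinded ones. The resulting artefact is m × D, about 0.01 to 0.12 category for assumed D of 0.2 to 0.3 and m of 5% to 40%. This supposes that the effect vanishes off drug and that the missing share is equal in both arms. The Week 12 displays of KCCQ-TSS change by PGIC or PGI-S category can also pair a carried rating with an observed KCCQ score. The primary and key secondary conclusions are unaffected.

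**What to change.** In SAP 5.1.2, delete the word conservative and replace the LOCF rule: summarise observed PGIC and PGI-S scores at each visit, with the number observed per arm, and carry no score past end of treatment.

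If a model is wanted for Week 12 PGI-S change, use a repeated-measures model under missing at random. The KCCQ model cannot simply be reused for PGIC: it analyses change from baseline with a baseline covariate, whereas PGIC rates change since the start of treatment and has no baseline. A PGIC model must omit that term.

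In SAP 5.4.2, restrict the displays of KCCQ-TSS change by PGIC or PGI-S response to participants with both measures observed at Week 12.

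The cost is a few lines of SAP text, and fewer participants at visits with missing scores.

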7. DISCONTINUATION OF STUDY INTERVENTION AND PARTICIPANT DISCONTINUATION/WITHDRAWAL

7.1. Discontinuation of Study Intervention

A participant's study intervention must be discontinued during the 3-month, double-blind treatment period if:

- the participant has started another SGLT2i
- the participant has been diagnosed with T1DM

- for safety reasons or tolerability reasons (eg, adverse event), it is in the best interest of the participant to discontinue study intervention
- the participant develops severe renal impairment or End Stage Renal Disease, or is on dialysis
- the participant becomes pregnant
- the participant develops diabetic ketoacidosis
- the participant develops a new active skin ulcer, osteomyelitis, gangrene, or critical ischemia of the lower extremity or has an amputation.

The participant may choose to discontinue the study intervention only and remain in the study. In this case, the participant will continue to perform assessments (KCCQ, PGI-S, PGIC) and allow continued passive data collection from the app, Fitbit, and medical claims. If contacted during the study, the call center or designee will inform the participant of the importance to the study and results to have ongoing ascertainment of assessments and vital status.

Additional information on informed consent for collection of vital status can be found in Section 10.2, Appendix 2: Regulatory, Ethical, and Study Oversight Considerations.

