Daily activity measurements via the Fitbit device will be collected continuously from the time study started (ie, when both the smartphone and the Fitbit are linked by a participant). Fitbit daily activity data will be aggregated into averages over 2-week intervals starting with a baseline period (ie, Baseline = average of Study Day 1 to Study Day 14) and similarly over the entire post-baseline study duration for each participant. This is to allow capturing a robust length of physical activity for each participant using the Fitbit device and minimizing variability associated with measurements in shorter time spans. The end-of-treatment (EOT) average value of the step count will be the average of the last 14 days prior to the last dose of study intervention, regardless of when the last dose is taken.

Claims data will be extracted as access to participant-level information becomes available. This will include clinical outcomes (including hospitalizations for HF and/or other reasons) coded using International Statistical Classification of Diseases and Related Health Problems (ICD)-9 and ICD-10 as appropriate.

Time windows will not be applied to summarize the safety data collected through claims. Self-reported safety data will be summarized through Week 12 (Day 87).

Table 1 presents the time windows and the target days for each time of measurement defined in the protocol.

Table 1: Measurement Windows

Parameter	Time Interval (label on output)	Time Interval (Day)*	Target Time Point (Day)
KCCQ (and its individual domains); PGIC and PGI-S; participant satisfaction survey	Screening/Baseline	-21 to <1	1
	Week 2	11 to 17	14
	Week 4	25 to 31	28
	Week 6	39 to 45	42
	Week 12	81 to 87	84
	Month 6	161 to 175	168
	Month 9	245 to 259	252
Daily Step Count / Daily Floors Climbed **	Baseline to Week 2	1 to 14	
	Week 3 & Week 4	15 to 28	
	Week 5 & Week 6	29 to 42	
	Week 7 & Week 8	43 to 56	

Parameter	Time Interval (label on output)	Time Interval (Day)*	Target Time Point (Day)
	Week 9 & Week 10	57 to 70	
	Week 11 & Week 12	71 to 84	
	
	Week 35 & Week 36	238 to 252	

*Relative to Study Day 1

** Measurements over a 2-week interval with ≥ 100 daily steps to allow capture of physical activity

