2.6. Baseline, End of Treatment, and End of Study

Baseline is defined as the last observation made prior to the start of the first study intervention administration. End of Treatment (EOT) observation will refer to the last observation made prior to and including the day of the last dose of study intervention, regardless of when the last dose is taken. For the PRO measurements, EOT observation will include the last observed value prior to the last dose of study intervention, and/or, within a measurement window allowed by the app that may overlap the last dose date (i.e., may extend the last dose date by a few days). For the daily

activity data, it will represent average from the last 14 days prior to the last dose taken, regardless of when the dose is taken.

The EOS value is defined as the observation that is taken on the date of very last available postbaseline data in the study period. Unscheduled measurement results are included in this definition and will be considered as the last timepoint value if the unscheduled measurement result is the last postbaseline result available within the analysis period.

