5.3. Secondary Endpoints

5.3.1. Definition

The first key secondary effectiveness endpoint is change in the daily step count from baseline to Week 12 averaged over two-week intervals. Even though evidence of a meaningful change in daily step count in chronic HF patients via Fitbit device is not readily available, there are several studies that have conducted six-minute walk tests (6MWT) among HF patients in general and examined a minimum clinically important difference in daily step counts under different conditions. A change of 30 meters¹⁰ (approximately 1000 steps) may be considered in the present study to be of clinical interest to benchmark the expected mean change in daily step count in this study over the double-blind treatment period. This expected mean change in daily step count will also be examined in relation to variables such as PRO measures (as anchors) and clinical outcomes to better characterize treatment effect on daily activity.

As HF patients are generally not consistent in their daily walk patterns, there will be variations in levels of their daily activity (whether it is a weekday or a weekend) as well as variability in the total wear time of the Fitbit device. As a rule, we will consider Fitbit recorded ≥ 100 steps¹³ taken in a day in the calculations of averages. This will ensure capturing any meaningful level of physical activity while avoiding even smaller variations in daily steps taken by a participant wearing a Fitbit device. For each participant, baseline daily step count will be calculated by averaging daily step counts from Study Day 1 through Study Day 14. All subsequent post-baseline daily step count data will also be averaged in 2-week intervals. The change from baseline to Week 12 in daily step count will be based on subtracting the average of daily step count for Week 11 and Week 12 from the baseline average for each participant. Additionally, daily step count data will be averaged in 3-, 5- and 7-day (1-week) intervals at baseline and throughout the treatment period respectively and corresponding changes from baseline will be calculated.

The variable daily floors climbed will also be aggregated in a similar fashion.

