5.3.2. Estimand

The first key secondary estimand to be estimated in the study, is defined by the following -

- Population: FAS (i.e., all randomized participants with HF who either have HF_rEF or HF_pEF, regardless of T2DM status with at least one dose of study intervention and at least 1 post-baseline KCCQ measurement)
- Treatment: canagliflozin 100 mg or placebo

- Variable: change from baseline to Week 12 in the daily step count averaged over 2-week intervals
- Intercurrent event: treatment discontinuations (either due to AE or other reasons) or treatment switching or temporary disruption in daily activity; use treatment policy strategy to address intercurrent events (i.e., use all available measurements collected during study, regardless of the occurrence of the intercurrent event); events of “loss to follow up” or “study withdrawal” or “death” are not considered intercurrent events but rather missing data.
- Population-level summary: difference in mean change from baseline to Week 12 in the daily step count averaged over 2-week intervals (i.e., difference is based on subtracting the average of daily step count for Week 11 and Week 12 from the baseline 14-day average daily step count) between two randomized groups.

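### For participants who stop drug early, the SAP's last-dose-anchored step-count rule conflicts with its treatment-policy Week 12 estimand, and the analysis section does not say which value is used

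*SAP*

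**What the plan says.** Two sets of provisions in the SAP bear on the Week 12 step-count value of someone who stops study drug early.

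**Treatment-policy provisions.** SAP 5.3.1 bases the change on "subtracting the average of daily step count for Week 11 and Week 12 from the baseline average for each participant". SAP 5.3.2 lists treatment discontinuation as an intercurrent event handled by treatment policy: "use all available measurements collected during study, regardless of the occurrence of the intercurrent event". SAP 2.3.2 includes assessments made after discontinuation in the full analysis set. Protocol 7.1 provides that participants who stop drug but remain in the study will "allow continued passive data collection from the app, Fitbit, and medical claims".

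**Last-dose-anchored provisions.** SAP 5.1.2 says that after premature discontinuation "the average of the last non-missing 14-day window prior to the last dose of study intervention will always be used as an EOT value". The window is (EOT-14, EOT-1) and is rolled back a day at a time until a valid one is found. The section adds: "This corresponds to a last observation carried forward (LOCF) up to Week 12/EOT approach". It then says that without at least 7 days of post-baseline activity data in a 14-day window, no EOT value is computed and the post-baseline value is missing. SAP 2.1 and 2.6 repeat the anchor: "average of the last 14 days prior to the last dose of study intervention, regardless of when the last dose is taken" and "average from the last 14 days prior to the last dose taken, regardless of when the dose is taken".

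SAP 5.3.3 specifies an MMRM and a two-sided t-test on 14-day averages at baseline and Week 12. It does not mention EOT.

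**The concern.** A value fixed before the last dose is a while-on-treatment value. A treatment-policy estimand asks for the Weeks 11-12 value whether or not drug was still being taken. The 5.1.2 rule makes no exception for participants whose Weeks 11-12 data were actually observed.

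Step count is the only secondary endpoint in the fixed-sequence test of SAP 1.3, so its derivation should leave no choice. As written, two programmers could derive different Week 12 values for the same early stopper. If the carried-forward value is used, any decline or recovery after stopping is ignored, and the analysis answers a different question from the stated estimand. If stopping, or activity after stopping, differs between arms, the treatment comparison is shifted.

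**Working it through.** The plan states no step-count SD, power or discontinuation figure to reproduce. The check is day arithmetic followed by an assumed range.

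**Inputs.** Baseline window: Days 1-14 (SAP 2.1, 5.1.2, 5.3.1). Week 12 window: Days 71-84 (SAP 2.1, Table 1). EOT window for last-dose day L: Days L-14 to L-1 (SAP 5.1.2). At least 7 days of post-baseline data are needed for an EOT value (SAP 5.1.2).

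**Step 1: overlap with Weeks 11-12.** The EOT window ends on Day L-1. It misses Days 71-84 entirely when L-1 ≤ 70, that is, L ≤ 71. For L from 72 to 84 the windows share L-71 days.

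**Step 2: overlap with baseline.** For L from 15 to 28 the window holds 29-L baseline days and L-15 post-baseline days. The 7-day condition, read as needing those days inside the window, requires L-15 ≥ 7, so L ≥ 22.

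With every day valid and no roll-back:

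| Last dose (L) | EOT window | Baseline days | Post-baseline days | Days shared with 71-84 | EOT value |
|---|---|---|---|---|---|
| 15 | 1-14 | 14 | 0 | 0 | missing |
| 18 | 4-17 | 11 | 3 | 0 | missing |
| 21 | 7-20 | 8 | 6 | 0 | missing |
| 22 | 8-21 | 7 | 7 | 0 | computed |
| 28 | 14-27 | 1 | 13 | 0 | computed |
| 29 | 15-28 | 0 | 14 | 0 | computed |
| 42 | 28-41 | 0 | 14 | 0 | computed |
| 71 | 57-70 | 0 | 14 | 0 | computed |
| 84 | 70-83 | 0 | 14 | 13 | computed |

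The conflict therefore matters for early stoppers and hardly at all for completers. Baseline days enter a computed EOT value for last doses on Days 22-28. The roll-back has no stated stop at Day 15, so a later stopper with gaps in wear could also be drawn back into baseline days.

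**Step 3: illustrative size.** Let q be the share of an arm that stops early but has Weeks 11-12 data. Let g be the EOT average minus the observed Weeks 11-12 average. Carrying forward shifts that arm's simple mean by q × g. The between-arm shift is q_cana × g_cana - q_pbo × g_pbo.

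Assumed ranges, not in the documents: q from 5% to 20%, g from 250 to 1,000 steps/day.

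- One arm: 0.05 × 250 = 12.5 to 0.20 × 1,000 = 200 steps/day.
- Between arms, equal q and equal g: 0.
- Between arms, 10% against 5%, g = 250: 25 - 12.5 = 12.5 steps/day.
- Between arms, 20% against 10%, g = 1,000: 200 - 100 = 100 steps/day.
- Between arms, 20% stopping and the fall in one arm only, g = 1,000: 200 steps/day.

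The sign reverses if activity recovers after stopping.

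**The case against.** The strongest reply is that EOT is a separate summary and never touches the Week 12 endpoint. SAP 5.3.1 to 5.3.3 define the endpoint, estimand and both analyses on Weeks 11-12 or Week 12 averages without naming EOT. SAP 5.1.2 keeps a record for every 2-week interval, with EOT and EOS values alongside, so an MMRM on those records could use the observed data. SAP 2.6 defines an EOT value for the patient-reported outcomes too, yet the KCCQ analysis still uses Week 12.

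This stands in part. A reader might infer that the plan settles on substitution and discards observed Fitbit data. The documents do not go that far, because no sentence says EOT replaces the Week 12 value and the interval records are retained. But the reply does not remove the conflict. SAP 5.1.2 ties EOT to Week 12 in its carry-forward label and treats a missing EOT as a missing post-baseline value. SAP 2.1 adds that the endpoint for analyses is the last recorded post-baseline data. SAP 5.3.3 gives EOT no other role. Substitution would enter most directly in the t-test, which uses one Week 12 value per participant.

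A reader might also infer that a last dose on Day 15 forces a change of zero, since that window is exactly Days 1-14. On its natural reading, the 7-day post-baseline condition makes the EOT value missing for last doses on Days 15-21.

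Finally, Protocol 7.1 lets participants remain in the study after stopping drug, but the documents give no retention or Fitbit-wear rate for them. How often Weeks 11-12 data would exist is unknown.

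**Conclusion.** The concern holds as an internal conflict with an unresolved consequence. The on-treatment carry-forward rule in SAP 5.1.2, echoed in 2.1 and 2.6, is incompatible with the treatment-policy Weeks 11-12 endpoint in 5.3.1 and 5.3.2 if it feeds that endpoint. SAP 5.3.3 does not say whether it does. If applied, it replaces observed Weeks 11-12 data for early stoppers who stay in the study, and it mixes 7 down to 1 baseline days into the EOT value for last doses on Days 22-28. The overlap figures rest on the natural reading of the 7-day condition and on no roll-back.

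The between-arm bias cannot be sized from the documents. They give no drug-discontinuation rate, post-stop activity or step-count SD. The 5% to 10% dropout in SAP 1.4 is a study-level figure, and the 1,000-step benchmark in SAP 5.3.1 concerns change over the treatment period, not loss after stopping. The figures in Step 3 are illustrations only, and a one-arm shift should not be read as treatment-effect bias. The between-arm effect is zero when stopping and post-stop activity are equal.

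**What to change.** - State in SAP 5.1.2 and 5.3.3 that the Week 12 value for step count and floors climbed is the observed Days 71-84 average for every participant, on or off drug.
- Apply the existing interval rule (missing if more than 7 of the 14 days are missing) and leave missing intervals to the MMRM.
- Keep the EOT carry-forward value only as a labelled while-on-treatment supplementary summary, with a window, including any roll-back, that excludes Days 1-14.
- Align SAP 2.1 and 2.6 by stating that the EOT value does not enter the Week 12 analyses.

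The cost is SAP wording and a simpler derivation, with no new data. The downside is that early stoppers without enough Fitbit data in Weeks 11-12 become missing instead of carried forward. They would drop out of the t-test and rely on the missing-at-random assumption in the MMRM.
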